## Abstract

The remodeling of the alveolar bone following tooth extraction results in significant bone loss at the extraction site. An excessive bone loss hampers the implementation of treatment plans, prediction of esthetic outcomes, and patient satisfaction. Placing bone substitute materials in an extraction socket may reduce the alveolar bone resorption. However, postoperative infection and inflammation are common side effects following bone graft surgeries. Finding a less invasive approach to preserve the alveolar ridge would be amenable to dental clinic. An animal study reported that bone density significantly increased in the extraction site with transcortical mini-screw placements, exhibiting markedly less atrophied alveolar ridge. In addition, the side effects from a mini-screw placement are minimal and no antibiotics are required. Therefore, we propose the placement of a transcortical mini-screw at the buccal plate of an extraction socket as a minimally invasive approach to preserve the alveolar ridge. The objective of this study is to determine the effects of transcortical mini-screws placed at the buccal plates of the extraction sockets in humans. We hypothesize that placement of a transcortical mini-screw at the buccal plate will significantly reduce bone loss at the site. To test this hypothesis, we are performing a prospective split-mouth design study. We are recruiting patients who need extraction of two maxillary premolars for orthodontic treatments. Cone beam computed tomography (CBCT) is exposed after the extraction of two premolars and before a transcortical mini-screw placement ( $T_0$ ). One 8-mm length mini-screw is placed at the buccal plate of the extraction socket on one side. The contralateral extraction socket is untreated. The mini-screw is removed at 6 months and the follow-up CBCT is obtained ( $T_6$ ). We will compare changes in the alveolar bone width at both extraction sides using the CBCTs. We predict that the placement of a transcortical mini-screw at the buccal plate of the extraction socket significantly reduces bone loss at the extraction site. Results of this study will offer a useful measure to sustain an edentulous alveolar ridge for a lengthy period without losing bone proper.

[figure not shown]

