## **APPROACH**

This is an on-going prospective clinical study under a protocol approved by the IRB (HP-00076020). Six subjects completed the study protocol. Interim data analysis was performed from these six subjects.

1. Sample size determination: The original sample size was determined to provide 80% power to recognize a significant difference of 1 mm between the two sides with a 95% confidence interval ( $\alpha=0.05$ ) and standard deviation of 1.0 mm, considering the difference in the mean width of the edentulous alveolar ridge as the primary outcome variable. Based on the power analysis reperformed by following the formula described by Faul et al using the interim data from the 6 subjects, 14 subjects will provide 80% power to recognize a significant difference of 0.5 mm in the width of the alveolar ridge between the two sides.

2. The Study Population: Patients with the following conditions are included: a) age  $\geq 18$  years, and b) two maxillary premolars (one from the left side and the other from the right side) required to be extracted in accordance with recommended dental treatment plans. Exclusion criteria are as follows: a) hyper-/hypothyroid dysfunctions, b) diabetes mellitus, c) subjects with a history of a chronic use of corticosteroid ( $> 6$  months), d) subjects with a history of taking oral/IV bisphosphonates within the past 2 years, e) smokers, and f) other systemic conditions influencing bone integrity.

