**4. Radiographic Measurements:** CBCT will be exposed after teeth extraction and before the mini-screw placement ( $T_0$ ). One mini-screw will be placed at the buccal plate of the extraction socket one week following the extraction of maxillary premolars in one side. The other extraction socket site will be untreated. At 6 months, the follow-up CBCT will be exposed for the maxilla after removal of the mini-screws. A blinded evaluator will measure the width of alveolar ridge on the CBCTs made at  $T_0$  and  $T_6$ . Changes in the width of alveolar ridge were measured from the outer wall at  $T_0$  to the outer wall at  $T_6$ . A positive value indicates bone loss. In the sagittal section, three levels will be determined by measuring from the crest to the apex and dividing the socket length into thirds. The measurements will be performed in coronal and axial sections (Figs 3a and 3b).

**Figure 3.** Measurements of bone loss after tooth extraction on CBCTs. (a-b) Examples of coronal (a) or axial (b) measurements. Changes of bone level from  $T_0$  to  $T_6$  was measured. Superimposition of two CBCT images ( $T_6$ , blue;  $T_0$ , grey) was performed using Invivo 6.0 software. Right side images present magnification of insets in left panels. (c-d) Changes in the width of alveolar ridge (mean  $\pm$  SD) in the experimental (exp) and the control (con) side at the crestal (C), middle (M), and apex (A) level in coronal or axial sections.

**5. Interim data and statistical analysis:** No inflammation and infection related to the mini-screw placements were observed in all 6 subjects. Miniscrews were removed at 6 months from 3 subjects and at 8 months from 3 subjects (the mean of 7-month) in keeping with planned dental treatments. Overall, the experimental side with the miniscrew placement showed less bone loss than the control side at the crestal, middle, and apex level in both coronal and axial measurements (Figs 3c and 3d). Upon completion of the study, a paired t-test will be performed to compare the changes in the width of alveolar ridge from the two sides. We will also measure mineral density distribution at the extraction sites from the two sides using CBCTs.

**6. Expected outcomes:** We predict that the experimental side with mini-screw placements will exhibit a significantly less bone loss than the control side. Bone density in the experimental side will be significantly greater than the control side.

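### The plan powers one primary ridge-width outcome, but does not say which of six CBCT width measures, or which average of them, the single paired t-test uses

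*Combined protocol and SAP*

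**What the plan says.** Approach, item 1 (sample size determination) defines the primary outcome by "considering the difference in the mean width of the edentulous alveolar ridge as the primary outcome variable", with 80% power and alpha 0.05. It then re-estimates the size from six interim subjects: 14 subjects for a 0.5 mm difference between sides. The Abstract points to CBCT as the modality: "We will compare changes in the alveolar bone width at both extraction sides using the CBCTs".

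Item 4 (Radiographic Measurements) sets out what is measured on CBCT. In the sagittal view "three levels will be determined by measuring from the crest to the apex and dividing the socket length into thirds", and "The measurements will be performed in coronal and axial sections".

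Item 5 (Interim data and statistical analysis) gives the whole of the planned width analysis: "a paired t-test will be performed to compare the changes in the width of alveolar ridge from the two sides". The same item reports that, overall, the screw side showed "less bone loss than the control side at the crestal, middle, and apex level in both coronal and axial measurements". The opening of the Approach confirms the look: "Interim data analysis was performed from these six subjects".

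Item 8 (Potential limitation) warns that the three levels may not all reach significance. It gives the crestal and middle levels importance for implants and the apex importance for orthodontics. It adds axial sections because palatal loss is hard to measure in coronal ones. No item ranks the levels or sections, or gives a multiplicity rule.

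**The concern.** A power statement and an alpha level belong to a particular test on a particular variable. Here the variable could be one level in one section, an average over levels in one section, an average over everything, or the group mean of any single measure. Two competent analysts could test different variables and both claim to follow the plan.

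Two features make this more than a missing detail. Item 8 discusses significance level by level and supplies a clinical rationale for each level, so a result at any one of them could be presented as the finding. Interim results by side on all six measures are also known, so a choice made now would be an informed one. At stake are the 5% error rate of the trial's main width comparison and the link between that comparison and the 14 subjects.

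**Working it through.** **Count of measures.** 3 levels (crestal, middle, apex) × 2 sections (coronal, axial) = 6 width changes per side, so 6 within-patient differences.

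**The plan's own figure.** Item 1 states n=14 for 0.5 mm at 80% power. The interim SD is not in the text and Figures 3c-d are not shown, so 14 can be neither confirmed nor refuted. It can be back-solved. For a paired t-test, noncentrality = (0.5/SD)×√14 with 13 degrees of freedom. Setting two-sided 5% power to 80% gives 0.5/SD = 0.810, so SD = 0.617 mm. If the calculation was one-sided, 0.5/SD = 0.702 and SD = 0.712 mm. The SD of 0.617 mm is used below as an assumption; the documents do not say which measure it would belong to.

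**Error rates with no true effect.** The documents give no correlations between measures, so equal correlations are assumed. Each patient's six differences are √ρ × (shared normal term) + √(1−ρ) × (own normal term); 200,000 trials per setting, n=14. Route A tests all six at two-sided 5% and counts any rejection. Route B picks the measure with the largest t in favour of the screw in the first six subjects and tests it in all 14, with those six included.

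| Assumed correlation | A: any of six | B: favouring screw | B: either direction |
|---|---|---|---|
| 0.5 | 21% | 7.3% | 7.5% |
| 0.7 | 17% | 5.9% | 6.4% |
| 0.9 | 11% | 4.3% | 5.4% |
| 0.95 | 9% | 3.8% | 5.3% |
| One measure fixed without regard to the interim | 5% | 2.5% | 5% |

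Independence would give 1 − 0.95⁶ = 26% for route A. This is only an upper reference, because measures on the same socket will be correlated.

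**Power of an average.** The mean of k measures has SD = 0.617 × √[(1+(k−1)ρ)/k].
- Three levels, one section: SD 0.504 mm (ρ=0.5) to 0.596 mm (ρ=0.9). A uniform 0.5 mm effect has 93% to 83% power. A 0.5 mm effect at one level only becomes 0.5/3 = 0.167 mm in the average and has 21% to 16% power.
- All six measures: SD 0.617×0.764 = 0.471 mm to 0.617×0.957 = 0.591 mm. The same noncentral t gives 96% to 83% power for a uniform effect. For an effect at one level in both sections (again 0.5/3 mm) it gives 23% to 16%.

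The choice of measure also moves the sample size. With 0.617 mm per measure, the six-measure average needs 10 subjects at ρ=0.5 and 14 at ρ=0.9.

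**The case against.** The strongest defence is that the plan does describe a single test. It has one primary variable, one paired t-test and one width prediction (item 6), and item 8 lists a limitation rather than a criterion for success. All of that stands, but it does not identify the variable.

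Several stronger readings are tempting, and the documents do not support them.
- A reader might infer that any significant level counts as success. No section says so.
- A reader might infer that the measure was, or will be, picked from the interim results. Item 1 attaches mean width to the original sample size, so its exact definition may have been settled before the look and simply not written here.
- A reader might conclude that no test lies behind the 14 subjects. Some interim SD must have produced that number; its source is unreported, not shown to be absent.
- A reader might take all six interim differences as consistent in every respect. The interim sentence is qualified as an overall statement, and the sizes are in a figure not shown.

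It is also fair to say that the error rates depend on assumed correlations. At 0.9 to 0.95, route B raises the total error only to 5.4% to 5.3%. The excess lies in the tail favouring the screw.

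**Conclusion.** The concern holds as a gap in the definition of the primary outcome. Six CBCT width measures are available, their interim results have been reported, and the plan does not say which one, or which average, is tested at alpha 0.05. That alone justifies a correction before further data are analysed.

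The inflated error rates (about 21% to 9% for any of six; about 7% to 4% in favour of the screw for an interim-chosen measure) describe routes that the text leaves open. They are not properties of a stated rule. They assume n=14, equal correlations of 0.5 to 0.95 and, for the second route, that the six interim subjects count among the 14, which the documents do not say. A measure fixed without regard to the interim results keeps 5%.

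**What to change.** In Section 5 of the Approach, state that the primary outcome is the within-patient difference (control minus experimental) in T0-to-T6 CBCT width change, averaged over the crestal, middle and apex levels and over both sections, tested once with a two-sided paired t-test at 0.05. If one section is preferred, name it on clinical grounds and address item 8's point that palatal loss is hard to measure in coronal sections.

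Make the individual level and section measures secondary, with Holm adjustment or with estimates and 95% confidence intervals only. Amend item 8 so that one significant level is not read as success on the primary question.

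Ask the sponsor:
- Was the measure fixed before the interim look, and where is that recorded? If it was fixed afterwards, disclose this.
- Which measure's SD gave 14 subjects? If it is not the named primary, restate the power.
- Do the six interim subjects count among the 14?

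The cost is wording only; no new measurement is needed. The amendment cannot undo the interim look. An average dilutes an effect confined to one level, as the power figures above show, but performs well if the effect is uniform. Holm over six secondary measures starts at 0.05/6 = 0.0083, where power for 0.5 mm on a single measure is about 50% at the assumed SD.

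A separate point needs reconciling with the T6 label: "Miniscrews were removed at 6 months from 3 subjects and at 8 months from 3 subjects".

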## **7. Research Related Risks**

Clinical risks for mini-screw are low. Overall failure rate of mini-screws is about 10% with orthodontic loading. Four to five weeks after the mini screw placement, failure rate dropped to 5%. Failures of mini-screw are mainly from loosen screws, which mean the mini-screws are mobile and are not firmly attached (or engaged) to the bone. Our incidence of loosen screws will be very low because the mini-screw will not be loaded for 6 months.

Some of the potential risks are as follows:

- Participants may experience inflammation, mild pain, or discomfort at the mini-screw site for about 2 days. Pain medication (Tylenol or Ibuprofen) will be enough to solve this problem.
- Infection rarely develops. If it occurs, antibiotics will be prescribed.
- The screw could become loose. If this occurs, the participant should contact the clinic immediately. We will remove the loosen screw and replace with a new one.
- The incidence of broken screws is very rare although a screw breaks might occur during the removal of a screw. A broken screw can be easily removed with an instrument.
- The mini-screw may not prevent bone loss.
- As with any study, there is a risk that the study data may not be kept confidential. We will minimize this risk by storing data in a secure location, such as a locked cabinet in a locked office. Electronic data will be password-protected.

**8. Potential limitation:** Not all measurements at the three levels may be significantly different. Preserving bone at the crestal and the middle level is critical in implant dentistry. Preserving bone at the apex level is clinically meaningful in orthodontics. It is difficult to measure bone loss in the palatal side with coronal sections of CBCTs. Therefore, we will also measure bone loss using axial sections of CBCTs. CT based bone density measurement may not be as accurate as direct measurement using bone biopsy. However, it is a very powerful non-invasive tool to measure mineral density.

## **9. Study period-time table for completion of the project**

Research procedures	5 months	6 months	1 month
Recruitments	X		
Research procedures	X	X	
Data analysis and preparing manuscript			X

